- Secondary outcome 3: What is the impact of the “Putting the Kitbags to work” programme on the **stress** (as measured by the “Stress in General” scale) of social workers and family support workers in teams randomly allocated to the intervention arm compared with social workers and family support workers in teams randomly allocated to the control arm? The outcome will be measured at month 6 and month 13 after intervention began.
- Secondary outcome 4: What is the impact of the “Putting the Kitbags to work” programme on the **number of sick days** taken by social workers and family support workers in teams randomly allocated to the intervention arm compared with social workers and family support workers in teams randomly allocated to the control arm from T1 to T13?

Foster carer outcomes:

- Secondary outcome 5: What is the impact of the “Putting the Kitbags to work” programme on the **self-efficacy** of foster and kinship carers supported by social worker teams randomly allocated to the intervention arm compared with foster carers supported by social worker teams randomly allocated to the control arm as measured? The outcome will be measured at month 6 and month 13 after intervention began. The population will be restricted to local authority employed foster carers only..

Design

Trial type and number of arms	Parallel multi-site cluster RCT (2 arms)
Unit of randomisation	Social Work Team (6-8 social workers)
Stratification variables (if applicable)	Local authority and team type (CIN+CP/CLA/Children with disabilities)

Participants

Oxfordshire County Council, the London Borough of Bexley, Haringey Council and Warwickshire County Council shall be participating in the trial.

Teams

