- for social workers and family support workers: the social worker or family support worker was a member of a team assigned to the intervention at point of randomisation and 0 else;
- for foster / kinship carers: the carer cares for a child or young person whose case is held at the point the foster carer enters the sample, by a social worker who is a member of a team assigned to the intervention at point of randomisation and 0 otherwise.

Although there is some turnover of social workers, family support workers and foster carers, about 80% of those at T0 (April 2021) will still be working with the local authority at T13 (May 2022), and so 80% will have received the full 12 months of the intervention. Binarising the treatment seems a reasonable proxy in this case.

For the outcomes relating to children, treatment is coded as a binary variable. When children enter the sample, at either the point of randomisation, or the point they become eligible (e.g. their case opens and meets other criteria) they will be allocated to treatment if the team of their allocated social worker was randomised to treatment.

Covariates

Including control variables increases the precision of the estimate. In each regression, we control for a number of relevant covariates. We outline different categories of covariates below.

Site effects

We include site fixed effects but not site-treatment interaction terms.

Previous outcome measures

We control for the previous measurements of the outcome variable where data is available. For the survey-based measures for social workers, family support workers and foster carers, the same measures will be asked at T6 (October 2021) and T13 (May 2022), and for administrative data we expect previous values to be available. For the outcomes of the CYP and parents / carers (including kinship carers), the previous measure of the outcome will be at T0 (April 2021) or when they entered services if they entered services after T0 (April 2021).

Other covariates

For CYP outcomes (primary outcome i) and secondary outcome i)), we include the following vector of individual-level covariates:

- gender (coded as male, female, or other/missing)
- age group (4-11, 12-17, 18 years, or missing with 4-11 as the reference category)
- ethnicity (Asian / Asian British, Black / African / Caribbean / Black British, Mixed / Multiple ethnic groups, Other ethnic group, White, missing; with the majority group as the reference category)

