- For each outcome, we will regress an indicator of missingness on the covariates in the main model (see the “Covariates” section) using logistic regression with standard errors clustered at the team level. If any of the coefficients on the covariates of the missingness model are statistically significant at the 5% level, then data is not missing completely at random (MCAR).
- In particular, we are interested in the coefficient on the treatment dummy. If it is not significant, this suggests that the data is missing experimentally at random (MEAR) (where data may be correlated with observable or unobservable variables, but not with treatment assignment) and we will only include observations for which we have the outcome data controlling for any variables which are significant (if they are not already specified in the “Covariates” section above).
- In line with WWCS statistical guidance, if the data on outcomes is missing experimentally not at random (MENAR) e.g. due to large differential attrition, then we will multiply impute within the treatment condition.

Sensitivity analysis following multiple imputation

Given that there may be a substantial proportion of outcome data to impute, we check the sensitivity of our results to the imputation strategy. We will:

²¹ See Taljaard, M., Donner, A., & Klar, N. (2008). Imputation strategies for missing continuous outcomes in cluster randomized trials. *Biometrical journal. Biometrische Zeitschrift*, 50(3), 329–345. <https://doi.org/10.1002/bimj.200710423>

- impute using baseline observation carried forwards (BOCF)
- impute using control drifted observation carried forward (CDOCF). This is done by carrying forward the baseline observation and then adding the “drift” from the comparator group to take into account the amount their outcome would have changed in the absence of treatment. The drift is calculated using an autoregression model for the comparator group.

Reporting

In addition to handling missing data and conducting sensitivity analyses, we also report some summary statistics to allow for a qualitative assessment of the impact of missing data on the treatment effect estimate.

- For each outcome and covariate, we will report the percentage of missing data alongside summary statistics
- Rates of loss to “post” data collection for the arms of the trial

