The interviews with foster carers will be semi-structured, via telephone or a virtual platform, and will last up to half an hour. Participants will be given the choice of platform between Zoom, Microsoft Teams and a phone call. Prior to the interview an information sheet will be shared with participants and the researcher will discuss the evaluation and measures taken to ensure confidentiality and privacy. The participant will have the chance to ask any questions and will be asked whether they consent to the interview being audio-recorded. If consent to record the call is not given, descriptive notes will be written by the researcher and written up following the call.

Interviews will be recorded, with consent, transcribed and pseudonymised prior to analysis.

Survey

A survey, asking different questions at different timepoints, will be shared with social workers and family support workers (including Kitbag Leads and team managers) from the eligible teams at T6 and T10-T13. The plan in v1 of the protocol was to send social workers and family support workers the survey at T1 instead of T6. The survey was delayed to allow social workers and family support workers to prioritise collecting the consents from the individual with parental responsibility and to avoid the confusion of too many forms.

The survey will help us to answer all four research questions and in particular we seek to understand:

- Confidence with using Kitbag
- How often social workers complete direct work with children and families
- The kinds of activities completed and the resources used for direct work
- How staff are supported to complete direct work with children and families
- How staff record direct work
- Whether staff feel supported to use Kitbag and how they are supported
- Frequency of use of Kitbag including whether some components are used more often than others
- Frequency of use of the Kitbag within the social worker team
- Support from team manager in supervision to use Kitbag

A survey will also be sent to foster and kinship carers in the intervention group at T6 and T10-T13. This will assess use of Kitbag and the outcome measure of self-efficacy.

Observation of workshops

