January 2021	Advisory Board meetings	UoS/IFF
January - March 2021	Site selection, engagement, set up meeting and work	All
March 2021	Ethics approval obtained	WWCS
March 2021	Randomisation of teams to kitbag	WWCS
April 2021	Kitbag leads identified and appointed	LA partners
Before data collection	Trial protocol drafted and published	WWCS
May 2021	Kitbag distribution	UoS/IFF

10th May 2021	Launch of project in 4 sites as one online event	UoS/IFF + LA partners
May 2021 - April 2022	Regular Kitbag use	LA partners
May 2022	Endline data collection	LA partners / WWCS
June - July 2022	Final analysis and report	WWCS

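### For the three survey outcomes the 'pre' covariate is a T6 score taken five months after Kitbags went out, so the T13 coefficient is not the full effect of the programme

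*Protocol*

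**What the plan says.** Under Previous outcome measures, the protocol states: "We control for the previous measurements of the outcome variable where data is available". The next sentence gives the survey times for social workers, family support workers and foster carers: "the same measures will be asked at T6 (October 2021) and T13 (May 2022"). The Survey section of the implementation and process evaluation explains the first date: "The plan in v1 of the protocol was to send social workers and family support workers the survey at T1 instead of T6". The same section gives T6 as the first survey for foster and kinship carers.

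The Timeline reads "May 2021 Kitbag distribution UoS/IFF", with regular use from May 2021 to April 2022. For secondary outcomes 2, 3 and 5, Research questions says: "The outcome will be measured at month 6 and month 13 after intervention began". The T6 score is therefore an outcome there and the available previous measure in the analysis plan.

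The Regression specification enters the covariate as Y_ict0 and describes it as the 'pre' outcome at t0. The Models paragraph reads the treatment coefficient as the impact of the intervention.

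Two statements do not fit the T6 date. For children and parents or carers, "the previous measure of the outcome will be at T0 (April 2021"), or at entry to services if later. The Data collection schedule still lists the survey at T1 and T13.

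Under Missing data strategy, numerical covariates, including pre-outcome measures, are multiply imputed. Covariates with more than 30% missing are dropped. One sensitivity analysis is to "impute using baseline observation carried forwards (BOCF"), and another adds a drift estimated in the comparator group to the same value.

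**The concern.** A covariate measured after treatment starts can itself be changed by treatment. Here it is an earlier reading of the same scale. If Kitbag has moved self-efficacy or stress by October 2021, holding the October score fixed takes out part of the effect that the May 2022 comparison is meant to show. The coefficient then no longer answers the research question, which compares arms as randomised.

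Three of the five secondary outcomes are at stake: worker self-efficacy, worker stress and carer self-efficacy. A programme that works early could be reported as doing little for staff and carers.

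**Working it through.** **Timing.** Covariates and the Independent variable section fix T0 as April 2021 and T13 as May 2022 ("about 80% of those at T0 (April 2021) will still be working with the local authority at T13 (May 2022")). T6 is therefore October 2021, as stated. From May to October 2021 is 5 months; from October 2021 to May 2022 is 7 months. T6 lies inside the period of regular use.

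**Formula.** Let d6 and d13 be the arm differences at T6 and T13, and b the within-arm slope of the T13 score on the T6 score. In a regression of T13 on arm and T6, the treatment coefficient is expected to be d13 − b·d6. The share of the T13 effect retained is 1 − b·(d6/d13).

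**Inputs.** The protocol gives neither b nor d6/d13, so both are assumed. The nearest figure is the test-retest reliability of .73 quoted for the carer scale, used below only as one illustrative value of b.

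| d6/d13 | b = 0.3 | b = 0.5 | b = 0.73 | b = 0.8 |
|---|---|---|---|---|
| 0 | 100% | 100% | 100% | 100% |
| 0.25 | 92.5% | 87.5% | 81.8% | 80% |
| 0.5 | 85% | 75% | 63.5% | 60% |
| 1 | 70% | 50% | 27% | 20% |

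The ends of the range with some T6 effect are 1 − 0.3 × 0.25 = 0.925 and 1 − 0.8 × 1 = 0.20.

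**Simulation check** (400,000 individuals, true T13 effect 0.20 SD). Without the T6 score the estimates were 0.197 to 0.204. With it:
- d6/d13 = 0.5: 0.152 (b = 0.5) and 0.127 (b = 0.73).
- d6/d13 = 1: 0.099 (b = 0.5) and 0.056 (b = 0.73).
- d6 = 0, b = 0.5: 0.202, so nothing is lost.

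**Precision given up by dropping T6.** With equal variances and correlation r, and ignoring clustering, the standard error grows by 1/√(1 − r²). At r = 0.6 this is 1/√0.64 = 1.25; at r = 0.3 it is 1.05 and at r = 0.8 it is 1.67.

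**Signal against noise.** On the same approximation b = r, and dropping T6 gives the better ratio of effect to standard error when √(1 − r²) > 1 − r·(d6/d13), that is, when d6/d13 > (1 − √(1 − r²))/r. At r = 0.6 this is (1 − 0.8)/0.6 = 0.33; at r = 0.4 it is 0.21 and at r = 0.7 it is 0.41.

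**The case against.** - **The term may never enter the model.** The Data collection schedule assumes a 10% response rate. If answering at T6 and at T13 were independent, about 90% of T13 respondents would have no T6 score, well past the 30% limit. This stands as a reason why the harm is conditional. It does not mend the plan: the meaning of the coefficient would then depend on response rates and could differ between outcomes.
- **The text never says outright that Y_ict0 is the T6 score, and other lines give T0 or T1.** True, so this is an inference. It is a strong one: the sentence after the adjustment rule gives T6 and T13 as the survey times, and the Survey section puts the first worker and carer surveys at T6. No T0 survey is described. The T1 row in the schedule contradicts that section, so it would be too flat to say that the document nowhere mentions an earlier carer survey.
- **The effect at T6 may be small.** The protocol expects mainly online use of Kitbag in the initial months because of Covid-19. On the other side, the SDQ outcome treats four months as long enough for the minimum number of uses. The documents do not settle d6.
- **A reader might infer that the model estimates only the change after T6.** That would be so only with b = 1, a change score. With d6 = d13 the change is zero, yet the adjusted model still keeps 1 − b of the effect.
- **The carried-forward analyses are peripheral.** They follow multiple imputation of outcomes, which is planned only if missingness is related to arm. That limits how often this part matters.

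**Conclusion.** The plan is wrong as written for worker self-efficacy, worker stress and carer self-efficacy. The only score firmly placed before T13 is taken after treatment began, so a coefficient adjusted for it is about d13 − b·d6 and not the total impact that the protocol says it is.

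The size rests on assumptions: 92.5% down to 20% of the T13 effect remains for b of 0.3 to 0.8 and d6/d13 of 0.25 to 1, and all of it remains with no T6 effect. The documents do not support a claim that these outcomes are certain to be biased towards zero; that needs a positive b, an effect in the same direction by T6, and a T6 term that survives the 30% rule.

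Nor do they support the inference that the trial's main result is compromised. The child outcomes and days attended draw their previous values from administrative data. This should be corrected before analysis, but it is confined to three secondary outcomes.

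**What to change.** For these three outcomes:
1. Exclude the T6 score from the T13 models and from the imputed 'pre' measures.
2. Report T6 as an interim post-randomisation outcome, with T13 as the main one.
3. Keep the covariates already listed for each group under Other covariates, plus local authority, using values that treatment cannot have changed. The team characteristics are already taken at T0.
4. State that baseline-carried-forward and control-drift imputation cannot be run, because no pre-intervention value exists to carry forward.
5. Reconcile the T0, T1, T6 and t0 statements in Previous outcome measures, Regression specification, Survey and Data collection schedule.

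No new data are needed. The cost is the precision that the T6 score would have brought (standard error about 25% larger at r = 0.6, more at higher correlations) and the loss of two sensitivity analyses for these outcomes.

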MDES was determined by the Excel macro PowerUp⁸ for a 3-level fixed effects blocked cluster random assignment design with treatment at level 2 (BCRA3_2f). The three levels are individual (as we're detecting power for the primary outcome this is the child / young person), social worker team and local authority with treatment assigned at the social worker team level to 50% of the teams. One would not expect high intraclass correlation within teams themselves

⁸ Dong, N. and Maynard, R. A. (2013). *PowerUp!*: A tool for calculating minimum detectable effect sizes and sample size requirements for experimental and quasi-experimental designs. *Journal of Research on Educational Effectiveness*, 6(1), 24-67. doi: 10.1080/19345747.2012.673143

as cases aren't assigned to a team on the basis of similarity other than the level of social work involvement (child in need, child protection etc) (0.03). Baseline is expected to be highly predictive of endline SDQ score (0.8).

Outcome measures

The aim of Kitbag is to improve children's emotional literacy and ability to understand, express and regulate their emotions as well as improving their behaviour and relationships with others. The primary outcome measure is emotional and behavioural difficulties. The other outcomes are secondary outcomes.

Primary Outcomes

Child Outcomes

1i) Children's social care involvement

Given that we may have concerns about selection bias into the primary data collection, we shall also estimate the impact of the Kitbag programme on administrative outcomes which can be collected for all children and young people in the eligible population. Although children's social care administrative outcomes are more tangentially related to Kitbag and are also more difficult to change in a relatively light touch intervention, they have the benefit of not being subject to attrition bias. Kitbag will be delivered to children and young people with all levels of social work involvement, and the logic model does not suggest that it will be particularly beneficial for children and young people with particular children's social care profiles. The third secondary outcome measure is the level of children's social care involvement (2iii). Specifically, this is operationalised as the sum of escalations and de-escalations over the course of the intervention (May 2021 - May 2022):

- case closed
- child on child in need plan
- child on child protection plan
- child in care

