¹² Lundh, L.G., Wangby-Lundh, M., & Bjarehed, J. (2008). Self reported emotional and behavioral problems in Swedish 14 to 15-year-old adolescents: A study with the self-report version of the Strengths and Difficulties Questionnaire. *Scandinavian Journal of Psychology*, 49, 523–532.

¹³ <https://youthinmind.com/products-and-services/sdq/>

¹⁴ Scoring the Strengths & Difficulties Questionnaire for age 4-17. (2014).

<https://www.ehcap.co.uk/content/sites/ehcap/uploads/NewsDocuments/236/SDQEnglishUK4-17scoring-1.PDF#page=4>

¹⁵ Goodman A, Lamping DL, Ploubidis GB. When to use broader internalising and externalising subscales instead of the hypothesised five subscales on the Strengths and Difficulties Questionnaire (SDQ): data from British parents, teachers and children. *J Abnorm Child Psychol*. 2010 Nov;38(8):1179-91. doi: 10.1007/s10802-010-9434-x. PMID: 20623175.

¹⁶ Van den Broeck, A., Vansteenkiste, M., De Witte, H., Soenens, B., & Lens, W. (2010). Capturing autonomy, competence, and relatedness at work: Construction and initial validation of the Work-related Basic Need Satisfaction scale. *Journal of Occupational and Organizational Psychology*, 83(4), 981-1002.

¹⁷ Stanton, J. M., Balzer, W. K., Smith, P. C., Parra, L. F., & Ironson, G. (2001). A General Measure of Work Stress: The Stress in General Scale. *Educational and Psychological Measurement*, 61(5), 866–888. <https://doi.org/10.1177/00131640121971455>

more stress. The sixth secondary outcome measure is the mean of the responses for the 8 items¹⁸ where “no” is coded as 0, “?” is coded as 1.5 and “yes” is coded as 3 (2vi)¹⁹.

2iv) Days attended

The hypothesised lower stress may lead to fewer sick days of social workers. We measure this over the entire intervention period from T1 to T13. Instead of measuring the number of sick-days, we will instead measure the number of ‘days attended’ in work. This allows us to include social workers who leave their posts over the course of the trial - these individuals will be classified as absent every day after they leave. Excluding these participants from the absence analysis would risk biasing the results, as individuals’ likelihood to leave is correlated with their rate of sickness absence. The number of days not attended may include holidays and parental leave in addition to sickness absence. If possible, we will control for the number of days of holiday and parental leave.

Foster and kinship Carer Outcomes

2v) Self-efficacy

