As represented in the logic model, one of the hypothesised mechanisms is carer self-efficacy. We measure parental / carer self-efficacy - “the parents’ beliefs about their effectiveness in overcoming or solving specific parenting problems” - using the parental self-efficacy subscale of the “Me as a parent” scale. The subscale consists of 4 questions and has been validated for parents of children aged 6 months to 15 years old. The subscale has good internal reliability (Cronbach’s alpha of .75), good test-retest reliability (.73), and good convergent validity (Pearson $r = .63$, $p.001$ between the 4 items of the MaaP self-efficacy subscale and the 8 items of the efficacy subscale of the 17-item Parent Sense of Competence scale²⁰). The questions will be adapted to account for those in non-parental caring roles. The population will be restricted to local authority employed foster carers only as these are the foster carers whom we will be able to access.

Analysis plan

Primary and Secondary Analysis

Primary analysis estimates the impact of the programme on our primary outcomes, whilst secondary analysis estimates the impact of the programme on our secondary outcomes. As the approach is the same, we outline it jointly below.

Models

The dependent variables are continuous and we will use an OLS regression. The regression coefficient on the treatment variable is interpreted as the impact of the intervention on the dependent variable (in the units described in the “Outcomes” section). Please see the “Outcomes” section for the expected direction of the impact.

¹⁸ Yankelovich, & Broadfoot, & Gillespie, Michael & Guidroz, Ashley. (2012). The Stress in General Scale Revisited: A One-factor Structure.. *Stress and Health*. 28. 137-148. The items (p.144) are Demanding, Pressured, Calm (R), Many things stressful, Nerve-wracking, Hassled, More stressful than I’d like, Overwhelming where (R) means reverse coded.

¹⁹ The Scale is usually calculated as the sum; however, we use the mean to allow for non-response.

²⁰ Hamilton, V. Matthews, J. & Crawford, S. (2014). Development and Preliminary Validation of a Parenting Self-Regulation Scale: “Me as a Parent”. *Journal of Child and Family Studies*. 24. 10.1007/s10826-014-0089-z.

Independent variable of interest: treatment

For the outcomes of social workers, family support workers and foster carers, treatment is coded as a binary variable where treatment = 1 if:

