- disability status (Yes, No, Don't know/missing with No as the reference category)
- most recent type of CSC intervention (coded as :
 - Child in Need
 - Child Protection Plan
 - Looked After - LA fostering / kinship care
 - Looked After - IFA / other LA fostering other placement type
 - missing;
 - with Child in Need as the reference category)

- unaccompanied asylum seeking child (yes, no, or missing with no as the reference category)
- if possible, whether their social worker has changed over the intervention period (yes, no, missing with no as the reference category)
- for the primary outcome 1-3 only, the number of status changes within the intervention period (numeric: as per the children's social care interaction outcome variable)

For social worker and family support worker outcomes, we include the following individual-level covariates:

- gender (coded as male, female, or other/missing),
- role (social worker, family support worker, or missing; with social worker as the reference category)
- contract type (permanent, agency or missing; with permanent as the reference category)
- the number of years experience (Associated and Supported Year in Employment / years<1, 1≤ years<4, 4≤years<9, 9years<15, ≥15 with ASYE as the reference category)

We include the following team-level characteristics (measured at T0):

- team type as categorised in Table 1 above (CINP / CPP, CLA, children with disabilities with CINP / CPP as the reference category)
- team size (numeric)
- percentage social worker or family support worker (numeric)
- percentage permanent or agency workers (numeric)

For foster carers (where we can match the data):

- gender (coded as male, female or other/missing)
- employer (LA foster carer, employed by an independent fostering agency or another local authority, or missing; with LA foster carer as the reference category)
- number of years experience (numeric)

Where the foster carer answering the survey is different between pre and post intervention data collection (e.g. the foster carer who answered at baseline isn't available or no longer fosters the child), the post data will be collected from the available foster carer and their pre data will be recorded as missing. The data collected from the foster carer who answered at the pre data collection point will be discarded (we won't impute their outcome data).

Please see the regression specification.

Standard errors

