Children are clustered into sibling groups, households (e.g. with other children in foster care) and caseloads (i.e. a group of children have the same social worker) and social worker teams. Because of this clustering, observations within one group (sibling group, household etc) may be more similar with each other on various characteristics compared with observations in other groups violating the assumption of independence. When data is structured in this way, the estimation of the treatment effect remains unbiased but the standard errors may be misspecified, leading to problems with inference. To correct for this, standard errors will be clustered at the level of randomisation, the social worker team level, in line with WWCS statistical guidance. This also accounts for correlations between observations at lower levels of nesting.

Handling non-compliance

If CYP are transferred to another team (e.g. due to a change of status), it is possible that the team to which they are transferred was ineligible for participating in the programme or had a different intervention / comparator group allocation. If a social worker or family support worker changes teams, it is possible that their new team had a different intervention/ comparator allocation. For all our analysis, we will conduct intention to treat analysis where a CYP is considered as treated if they are / were supported by a social worker who is a member of an intervention team at the point they entered the sample (either at randomisation or when their case started), irrespective of their use of Kitbag.

Multiple Comparison Adjustments

We will adjust for multiple comparisons within the secondary outcomes using Hochberg's step-up procedure, as per WWCS statistical guidance.

Regression specification

For social workers, family support workers and foster carer outcomes:

$$Y_{ict13} = \beta_0 + \beta_1 D_c + \beta_{2:4} A_c' + \beta_5 Y_{ict0} + \beta_{6:k+6} X_i' + \beta_{k+6:k+11} M_c' + \epsilon_c$$

Where:

- Y_{ict13} is the dependent variable for individual i , team c at the end of the trial, $t13$. β_0 is the intercept
- D_c is the treatment variable
- A_c is a vector of the local authority fixed effects
- Y_{ict0} is the "pre" outcome of individual i in team c , at their "pre" data collection point, $t0$
- X_i' is an $N \times k$ matrix of characteristics of individual i
- M_c' is an $N \times 5$ matrix of characteristics of team c
- ϵ_c is the error term clustered at the team level c

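### The child-outcome models adjust for a change of social worker during the trial, which can follow from the primary outcome or from treatment, so the treatment coefficient is no longer the total effect

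*Protocol*

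**What the plan says.** The Protocol, under Covariates (Other covariates), introduces the list with: "For CYP outcomes (primary outcome i) and secondary outcome i)), we include the following vector of individual-level covariates". One item is "if possible, whether their social worker has changed over the intervention period", coded yes, no or missing. The child-outcome equation under Regression specification carries this individual-level vector into the model.

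The primary outcome is defined under Outcome measures (1i): "this is operationalised as the sum of escalations and de-escalations over the course of the intervention", May 2021 to May 2022, with each step up scored +1 and each step down −1. A fall counts as benefit.

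Under Models: "The regression coefficient on the treatment variable is interpreted as the impact of the intervention on the dependent variable". Under Handling non-compliance: "For all our analysis, we will conduct intention to treat analysis". The only reason given for adjusting is precision. Nothing marks the worker-change item as a mediation or sensitivity analysis. The team-level covariates, by contrast, are fixed at T0.

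**The concern.** A covariate that improves precision without changing what is estimated has to be unaffected by treatment. Worker change over the trial year may be affected in two ways.

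- **Through the outcome.** Handling non-compliance says: "If CYP are transferred to another team (e.g. due to a change of status". The team types are "team type as categorised in Table 1 above (CINP / CPP, CLA, children with disabilities", so a move into or out of care crosses a team boundary and can bring a new worker. Closure may work the other way, since a closed case leaves fewer months in which a worker can change.
- **Through staffing.** Section 2iv says: "The hypothesised lower stress may lead to fewer sick days of social workers". It also ties the likelihood of leaving to sickness absence. If the programme altered turnover, it would alter this covariate directly.

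In either case the regression compares children with the same worker-change status, and some of the programme's effect can be credited to the covariate. The primary estimate is at stake. The exploratory child models reuse the same covariates, and the cost evaluation counts only outcomes significant at 5%.

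The count of status changes in the same list is a separate item. Deleting it would leave this problem in place.

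**Working it through.** **The plan's own figure.** The protocol gives no rates for worker change, escalation or closure by arm, so it has no figure for this point. Its MDES of 0.127 SD does not enter the argument. For completeness, the stated inputs give sqrt[0.03 × 0.9/(0.25 × 60) + 0.97 × 0.2/(0.25 × 60 × 150)] = 0.0434. Multiplied by 2.859 (t quantiles, 49 df) this is 0.124, close to the stated value.

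**Formula.** Let Y be the outcome, D treatment and W worker change. In least squares with D and W:

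adjusted coefficient = total effect − b × [P(W | treated) − P(W | control)],

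where b is the pooled within-arm slope of Y on W. With equal arms, b is the sum of the two within-arm covariances divided by the sum of the two within-arm variances of W. The two coefficients agree only if b or the difference in P(W) is zero.

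**One case in full (all rates assumed).** Y is +1, −1 or 0. Escalation falls from 15% to 9%; closure is 25% in both arms. W occurs in 90% after escalation, 10% after closure and 20% otherwise.

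- P(W), control: 0.15 × 0.9 + 0.25 × 0.1 + 0.60 × 0.2 = 0.280.
- P(W), treated: 0.09 × 0.9 + 0.25 × 0.1 + 0.66 × 0.2 = 0.238.
- Covariance, control: (0.135 − 0.025) + 0.10 × 0.280 = 0.1380. Treated: (0.081 − 0.025) + 0.16 × 0.238 = 0.0941.
- Variance of W: 0.2016 and 0.1814.
- b = 0.2321/0.3830 = 0.606.
- Adjusted coefficient = −0.060 + 0.606 × 0.042 = −0.0345, which is 58% of the true effect.

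**Range of assumed cases, same formula.** W rates are after escalation / closure / no change.

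| Control to treated | W rates (%) | P(W), control to treated | b | Total | Adjusted |
|---|---|---|---|---|---|
| Escalation 10 to 7%, closure 40 to 43% | 60/10/20 | 0.200 to 0.185 | 0.469 | −0.060 | −0.0530 (88%) |
| Escalation 15 to 9%, closure 25% | 90/20/20 | 0.305 to 0.263 | 0.465 | −0.060 | −0.0405 (67%) |
| Closure 40 to 46%, escalation 10% | 60/20/20 | 0.240 to 0.240 | 0.292 | −0.060 | −0.0600 (100%) |
| Closure 40 to 46%, escalation 10% | 60/60/20 | 0.400 to 0.424 | −0.255 | −0.060 | −0.0539 (90%) |
| Escalation 10 to 4%, closure 40% | 60/60/20 | 0.400 to 0.376 | −0.296 | −0.060 | −0.0671 (112%) |
| No effect (15%, 25%); W 5 points lower if treated | 60/20/20 | 0.260 to 0.210 | 0.368 | 0 | +0.0184 |
| No effect (15%, 25%); W 5 points lower if treated | 60/10/20 | 0.235 to 0.185 | 0.535 | 0 | +0.0268 |

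Two further cases score entry to care as +2.

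- **Large loss.** Care entry 15% to 10%, closure 45%, W rates 95/10/20: P(W) goes from 0.2675 to 0.2300. b = (0.2801 + 0.2025)/(0.1959 + 0.1771) = 1.294. Adjusted = −0.100 + 1.294 × 0.0375 = −0.0515, a loss of about 48%.
- **Small loss.** Care entry 3% to 2%, child-in-need to child-protection moves 10% to 8% (+1, within one team), closure 40%, W 90% after care entry and 20% otherwise: P(W) goes from 0.221 to 0.214, and −0.040 becomes −0.0384, a loss of 4%.

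These cases omit the other planned covariates, including baseline status. They show the mechanism and its possible size; they do not forecast it.

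**The case against.** Several stronger readings are tempting, and the protocol does not support them.

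- **That a status change always brings a new worker.** The protocol gives it only as an example of why a child may be transferred. Child-in-need and child-protection cases share a team type, disability teams are not defined by status, and closure need not bring a new worker. The link is that a status change can lead to a worker change.
- **That the bias is always towards no effect.** Some cases above show no loss, and one gives 112%. When worker turnover alone differs by arm, the bias is a false signal of harm.
- **That a large loss is typical.** The largest losses need many care entries, a sizeable effect on them, and worker change in 90% or more of them. The protocol itself regards these administrative outcomes as harder to shift with a light-touch programme. With rarer care entry the loss was 4%.
- **That the programme is expected to reduce staff leaving.** Section 2iv hypothesises less stress and fewer sick days and notes that absence and leaving are correlated. It stops short of predicting less leaving, so the staffing route is a possibility.
- **That SDQ is affected equally.** That population has been looked after without a break for at least a year, so the status-change route largely falls away. What remains is a possible mediator, with no calculation behind it.
- **That intention to treat is abandoned.** The protocol's definition concerns how children are classified, and that is untouched. The conflict is with reading the coefficient as the programme's impact.

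These points limit the certainty, direction and size of the bias. They do not make the adjustment valid. The words if possible make inclusion depend on data availability, and also leave the content of the primary model open.

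**Conclusion.** The point holds in this form: the primary child model includes a variable measured after randomisation that the outcome can cause and that treatment might affect, yet its treatment coefficient is read as the total impact. That reading is secure only if worker change is equally common in both arms or unrelated to the outcome within arms, and the protocol gives no ground for assuming either.

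The bias is often towards zero. Under assumed rates it ranges from no loss to about 48% of the effect, can overshoot to about 112%, and can give roughly +0.02 to +0.03 under the null if turnover is 5 points lower in the intervention arm. None of these figures can be derived from the protocol. For SDQ the concern is weaker and rests mainly on possible mediation.

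**What to change.** Delete the worker-change item from the covariates for the primary and SDQ models, and keep only covariates fixed at or before the child's entry to the sample. Report worker change by arm descriptively as a process measure; if an adjusted model is still wanted, label it exploratory and do not read its coefficient as the programme's impact.

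This removes one line from the plan and needs no new data. The cost is at most a small loss of apparent precision.
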